2.3.1.5 American college of rheumatology (ACR) response criteria

This efficacy variable is the clinical response to treatment according to ACR improvement criteria. A patient will be considered a responder according to ACR20 criteria if she/he fulfills all following three criteria:

- at least 20% improvement from baseline in tender joint count, using the 68-joint count
- at least 20% improvement from baseline in swollen joint count, using the 66-joint count
- and at least 20% improvement from baseline in at least 3 of the following 5 measures:
 - Patient's assessment of RA pain (VAS 100 mm)
 - Patient's global assessment of disease activity (VAS 100 mm)
 - Physician's global assessment of disease activity (VAS 100 mm)
 - Patient self-assessed disability (Health Assessment Questionnaire [HAQ] Disability Index)
 - CRP or ESR

ACR50 and ACR70 are defined as ACR20 replacing '20% improvement' by '50% improvement' and '70% improvement' respectively.

The ACR criteria will be calculated for Week 4, Week 12, Week 24 and Week 48 (Visits 1, 2, 4, 8, 14 and 16).

2.3.1.6 Boolean remission

Boolean remission is defined as TJC28 \leq 1 and SJC28 \leq 1, CRP level (mg/dL) \leq 1, and PtGA (VAS 100 mm) \leq 10.

If any of the TJC28, SJC28, CRP, or PtGA are missing then the Boolean remission is missing.

2.3.1.7 Patient's assessment of RA pain

The patient's assessment of pain was to be assessed by the patient as defined in the protocol at screening, baseline, Week 2, Week 4, Week 12, Week 24 and Week 48 (Visits 1, 2, 3, 4, 8, 14 and 16) using 100 mm visual analog scale (VAS) ranging from 'no pain' to 'unbearable pain'.

2.3.1.8 Patient's global assessment of disease (PtGA)

The patient's global assessment of disease activity will be assessed by the patient as defined in the protocol at screening, baseline, Week 2, Week 4, Week 12, Week 24 and Week 48 (Visits 1, 2, 3, 4, 8, 14 and 16) using 100 mm VAS ranging from "very good" to "very poor"..

2.3.1.9 Physician's global assessment of disease activity (PhGA)

The physician's global assessment of disease activity will be assessed by the investigator as defined in the protocol at screening, baseline, Week 2, Week 4, Week 12, Week 24 and Week 48 (Visits 1, 2, 3, 4, 8, 14 and 16) using 100 mm VAS ranging from "very good" to "very poor",

2.3.1.10 Health-related quality of life disability index (HAQ-DI)

The patient health assessment questionnaire disability index, HAQ-DI, will be used to assess physical ability and functional status of patients as well as quality of life.

HAQ-DI assessments will be done at Baseline, weeks 4, 12, 24, and 48 or, if applicable, at End of Study Visit.

The HAQ-DI consists of 20 questions, or items, which are grouped into 8 categories, or sections, of functioning in performing 8 common activities of daily living (with 2 or 3 questions in each category). Scoring within each section is from 0 (without any difficulty) to 3 (unable to do). For each section the score given to that section is the worst score within the section, i.e. if one question is scored 1 and another 2, then the score for the section is 2. In addition, if an aide or device is used or if help is required from another individual, then the minimum score for that section is 2. If the section score is already 2 or more then no modification is made.

Table 2-3 HAQ-DI items and aids

Section	Daily activity	Items	Aids and help
1	Dressing and grooming	(1) able to dress yourself (2) able to use shampoo	Devices used for dressing, Help dressing or grooming
2	Arising	(1) able to stand up from straight chair (2) able to get out of bed	Special or built up chair, help arising
3	Eating	(1) able to cut your meat (2) able to lift a full cup or glass to your mouth (3) able to open a new milk carton	Built up or special utensils, help eating
4	Walking	(1) able to walk outdoors on flat ground (2) able to climb up five steps	Cane, Walker, Crutches, Wheelchair, help walking
5	Reaching	(1) able to reach down to get a 5 pound object from just above your head (2) able to bend down to pick up clothing from the floor	Long-handled appliances for reach, help reaching

Section	Daily activity	Items	Aids and help
6	Hygiene	(1) able to wash and dry your body (2) able to take a tub bath (3) able to get on and off the toilet	Bathtub bar, Bathtub seat, Long-handled appliances in bathroom, Raised toilet seat, help with hygiene
7	Gripping	(1) able to open car doors (2) able to open jam jars which have been previously opened (3) able to turn faucets on and off	Jar opener, help with gripping and opening things
8	Activities	(1) able to run errands and shop (2) able to get in and out of a car (3) able to do chores such as vacuuming or yardwork	Help with errands and chores

The 8 scores of the 8 sections are summed and divided by 8 to provide the total HAQ-DI score. The range for this score is (0, 3). In the event that one/two sections are not completed by a patient then the summed score would be divided by 7/6. The HAQ-DI total score is not computed when the patient provides answers in fewer than 6 categories.

2.3.1.11 Functional assessment of chronic illness therapy - fatigue scale (FACIT- Fatigue)

The Functional Assessment of Chronic Illness Therapy – Fatigue Scale (FACIT-Fatigue) is a 13- item questionnaire that assesses self-reported fatigue and its impact upon daily activities and function. FACIT assessments will be completed by the patient at Baseline, weeks 4, 12, 24, and 48 or, if applicable, at End of Study Visit.

Table 2-4 FACIT Fatigue scale scoring

No	Code	Question	Not at all	A little bit	Some-what	Quite a bit	Very much
1	HI7	I feel fatigued	4	3	2	1	0
2	HI12	I feel weak all over	4	3	2	1	0
3	An1	I feel listless ("washed out")	4	3	2	1	0
4	An2	I feel tired	4	3	2	1	0
5	An3	I have trouble starting things because I am tired	4	3	2	1	0
6	An4	I have trouble finishing things because I am tired	4	3	2	1	0
7	An5	I have energy	0	1	2	3	4
8	An7	I am able to do my usual activities	0	1	2	3	4
9	An8	I need to sleep during the day	4	3	2	1	0
10	An12	I am too tired to eat	4	3	2	1	0

No	Code	Question	Not at all	A little bit	Some-what	Quite a bit	Very much
11	An14	I need help doing my usual activities	4	3	2	1	0
12	An15	I am frustrated by being too tired to do the things I want to do	4	3	2	1	0
13	An16	I have to limit my social activities because I am tired	4	3	2	1	0

Items are scored as follows: 4=Not at All; 3=A little Bit; 2=Somewhat; 1=Quite a bit; 0=Very much, except for items number 7 and 8 which are reverse scored.

Each of the 13 items of the FACIT-Fatigue scale ranges from 0-4 (0 is the worst response), and are equally scaled so that the range of possible FACIT Fatigue scores is 0-52, with 0 being the worst possible score and 52 the best.

In cases where some answers may be missing, a total score is prorated from the score of the answered items, so long as more than 50% of the items (i.e., at least 7 of 13) were answered.

2.3.1.12 Rheumatoid factor and anti-CCP antibodies

Rheumatoid factor and anti-CCP antibodies assessment as a measure of RA serological status will be performed at screening, week 12, week 24, week 48 / End of Study visit. Rheumatoid factor values \leq 10 UI/mL and anti-CCP antibodies values $<$ 17 U/mL are considered negative, otherwise positive.

2.3.2 Safety and tolerability assessments

2.3.2.1 AEs

An adverse event is the appearance or worsening of any undesirable sign, symptom, or medical condition occurring after starting the study drug even if the event is not considered to be related to study drug. Study drug includes the investigational drug under evaluation and the comparator drug that is given during any phase of the study. Medical conditions/diseases present before starting study drug are only considered adverse events if they worsen after starting study drug. Abnormal laboratory values or test results constitute adverse events only if they induce clinical signs or symptoms, are considered clinically significant, or require therapy.

Adverse events will be coded using MedDRA version 20.0.

Treatment emergent AEs (TEAEs) are events started after the first dose of study treatment and before study discontinuation or 30 days after last dose, whichever occurs later. In case where it is not possible to define an AE as TEAE or not, the AE will be classified by the worst case, i.e. treatment emergent.

All adverse events with start date on or after the date of the first study medication in SP2 will be counted as belonging to Study Period 2. In the case of a partial start date see [Appendix 1](#) on how such cases will be handled. If it is unclear whether the AE belongs to SP1 or SP2 then the AE will be assigned to SP2. This is a conservative approach since all patients are treated with the investigational product GP2017 in SP2.

Adverse events of special interest are defined as a subset of TEAE in [Appendix 3](#).

The investigator or qualified designee will have recorded ISRs belonging to one of the following: injection site erythema, injection site haematoma, injection site induration, injection site inflammation, injection site nodule, injection site oedema, injection site pain, injection site pruritus, injection site rash or injection site discolouration at the specified time points. Incidence and occurrence of ISRs and symptoms will be calculated.

All ISR are considered as a subgroup of TEAE. An ISR that fulfills the criteria of an SAE will be documented and reported as such.

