- Suspected: The temporal relationship of the clinical event to trial drug administration makes a causal relationship possible, and other drugs, therapeutic interventions or underlying conditions do not provide a sufficient explanation for the observed event.
- If the event is due to lack of efficacy or progression of underlying illness (i.e. progression of the study indication) the assessment of causality will usually be 'Not suspected'. The rationale for this guidance is as follows:
  - the symptoms of a lack of efficacy or progression of underlying illness are not caused by the trial drug, they happen in spite of its administration
  - both lack of efficacy and progression of underlying disease can only be evaluated meaningfully by an analysis of cohorts, not on a single patient

3. its duration (start and end dates or if continuing at final exam)
4. whether it constitutes a serious adverse event (SAE) (see Section 7.2.1 for definition of SAE)

**Unlike routine safety assessments, SAEs are monitored continuously and have special reporting requirements; see Section 7.2.**

5. action taken

All adverse events should be treated appropriately. Treatment may include one or more of the following: no action taken (i.e. further observation only); study drug dosage adjusted/temporarily interrupted; study drug permanently discontinued due to this adverse event; concomitant medication given; non-drug therapy given, patient hospitalized/patient's hospitalization prolonged. The action taken to treat the adverse event should be recorded on the Adverse Event CRF.

6. Its outcome (not recovered/not resolved; recovered/resolved; recovering/resolving, recovered/resolved with sequelae; fatal; or unknown)

Once an adverse event is detected, it should be followed until its resolution or until it is judged to be permanent, and assessment should be made at each visit (or more frequently, if necessary) of any changes in severity, the suspected relationship to the study drug, the interventions required to treat it, and the outcome.

Information about common side effects already known about the investigational drug can be found in the IB or will be communicated between IB updates in the form of Investigator Notifications. This information will be included in the patient informed consent and should be discussed with the patient during the study as needed.

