#### **Adverse events**

Treatment Emergent AEs (TEAE) defined as events started after the first dose of study treatment or events present prior to the first dose of study treatment but increased in severity, will be summarized. However all AEs recorded will be listed.

AEs will be summarized by primary system organ class and preferred term for:

- TEAEs
- TEAEs by maximum severity
- Treatment-related TEAEs
- SAEs
- TEAEs leading to dose adjustment/interruption
- TEAEs leading to premature discontinuation
- deaths

If a patient reported more than one adverse event within the same primary system organ class/preferred term, the patient will be counted only once with the greatest severity at the system organ class level/preferred term, where applicable.

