4.6.2.1.1 Summary of AEs by severity

Severity is classified as mild/moderate/severe (increasing severity). Treatment emergent AEs starting after the first dose of study medication with a missing severity will be classified as severe. If a patient reports a TEAE more than once within that SOC/PT, the TEAE with the highest severity will be presented.

4.6.2.1.2 Summary of study treatment related AEs.

Relationship, as indicated by the investigator, is classed as suspected/not suspected/not applicable (before study drug administration). A related TEAE is defined as a TEAE with a relationship to study medication as “suspected” to study medication. Treatment emergent AEs with a missing relationship to study medication will be regarded as “suspected” to study medication. If a patient reports the same TEAE more than once within that SOC/PT, the TEAE with the worst case relationship to study medication will be presented.

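### The SAP drops worsening of pre-dose events from the TEAE definition without declaring it and, separately, has no rule for adverse events that worsen after the Week 24 switch

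*SAP*

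**What the plan says.** **Definition of treatment-emergent.** Protocol 9.5.3 has two limbs: events that start after the first dose, and "events present prior to the first dose of study treatment but increased in severity". SAP 2.3.2.1 has one: "Treatment emergent AEs (TEAEs) are events started after the first dose of study treatment and before study discontinuation", with the window running to 30 days after the last dose if that is later. An event that cannot be classified is taken as treatment-emergent. SAP Section 3, which sets out changes to planned analyses, covers additional change-from-baseline analyses, entire-study analyses, more detail on power, and joint imputation. It does not mention the TEAE definition.

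**Period assignment.** Under SAP 2.3.2.1, "All adverse events with start date on or after the date of the first study medication in SP2" belong to Study Period 2. SAP 4.1.2 puts events that start on the first day of Period 2 into Period 2. Appendix 1 does the same for partial start dates that could fall in either period. All three rules work on the start date.

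**Recording.** Protocol 7.1 follows each event to resolution, or until it is judged permanent, and says that "assessment should be made at each visit (or more frequently, if necessary) of any changes in severity". Protocol 7.2.2 has progression of an SAE reported as follow-up to the original episode.

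**Tables.** SAP 2.1.2 gives Period 2 the columns Continued GP2017 and Humira to GP2017. For the entire study, the switched patients sit in one pooled Humira/Switched GP2017 column.

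**The concern.** There are two separate gaps.

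The first is an undeclared difference between protocol and SAP in a core safety definition. A programmer working from the SAP would leave out events that the protocol promised to summarize.

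The second concerns the purpose of Study Period 2. Protocol 2.2 sets the aim of evaluating the incidence and severity of adverse events in patients who continue on GP2017 and in those who switch to it. Worsening of an event already under way is one form that a tolerability problem after a switch could take. If the period is fixed by onset alone, the Period 2 tables may be unable to show it, including the by-period summaries of SAEs and of events leading to discontinuation (SAP 4.6.2.1.3).

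**Working it through.** No figure in the plan needs reproducing. The check sets the rules side by side and follows two cases through them.

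**Case A: event with a known start before the first dose that worsens on study drug.**
- Protocol 9.5.3: treatment-emergent, by the second limb.
- SAP 2.3.2.1: not treatment-emergent, because it did not start after the first dose. The worst-case default does not help, since the start date is known.
- Can it arise? SAEs are collected from informed consent (Protocol 7.2.2 and the Table 6-1 footnote), and SAE progression is follow-up to the original episode. A screening SAE in a patient who is later randomized, and which then worsens, would naturally keep its pre-dose start date.

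**Case B: event that starts in Period 1 and worsens after the first Period 2 dose.**
- It started after the first dose of study treatment, so it is a TEAE under both definitions. The dropped limb plays no part here.
- Kept on one record, it has a Period 1 start date and is counted in Period 1 only. It is absent from Humira to GP2017 or, in the other arm, from Continued GP2017.
- Entered as a new event dated at the worsening, it is counted in Period 2.
- The documents do not say which happens for non-serious events. For SAEs, the follow-up rule points to one continuing record.
- Either way it is in the entire-study tables, but those do not separate time before and after Week 24.

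**Size of Case B (illustrative).**
- Patients randomized to Humira: 154 (Protocol 5.2).
- Anticipated dropout: 20% (Protocol Section 4). If all of it falls before Week 24: 154 × 0.80 = 123.2, about 123 switching.
- Assumed share with an event ongoing at the switch: 20% to 40%. Assumed share of those that worsen afterwards: 5% to 15%. Neither rate is in the documents. The sum treats each such patient as having one ongoing event, kept on one record.
- Low: 123 × 0.20 × 0.05 = 1.2.
- High: 123 × 0.40 × 0.15 = 7.4.

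This gives roughly 1 to 7 switched patients. Patients without at least a moderate response at Week 24 do not enter Period 2, which lowers the count. If part of the dropout falls after Week 24, the base rises towards 154 and the range towards 1.5 (154 × 0.20 × 0.05) to 9.2 (154 × 0.40 × 0.15). The same arithmetic applies to the continued arm.

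**The case against.** The strongest reply is that both gaps may be nearly empty.

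On Case A, the SAP keeps worsening in its definition of an adverse event, treats a pre-existing condition as an adverse event only if it worsens after study drug starts, and sends doubtful cases to treatment-emergent. If sites date such an event at the worsening, the missing limb changes nothing. That limits the size, but no section says that the start date is the date of worsening, and the omission remains undeclared.

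On Case B, the protocol defines emergence against the first study dose and never resets it at Week 24. The Period 2 safety objectives are to evaluate, not to test. A Period 2 worsening rule therefore adds to the plan; it does not correct a departure from the protocol. That is fair. The addition is still needed if the Period 2 tables are to describe severity after the switch. The SAP already lets medications that span the switch be reported in both periods (4.1.2, 4.3.3), with no counterpart for adverse events.

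A reader might infer three stronger things that the documents do not support:
- **That the missing limb causes the gap at the switch.** It does not. The limb refers to the first study dose, and restoring it would move no Case B event into Period 2.
- **That a worsening after the switch can never appear under GP2017.** This depends on one-record entry, which is not specified for non-serious events. Unclear start dates default to Period 2, and the entire-study tables include the event.
- **That its later grade is shown against Humira in Period 1.** SAP 4.6.2.1.1 does say that "the TEAE with the highest severity will be presented", but for a TEAE reported more than once within a system organ class or preferred term. It does not address change within one record.

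**Conclusion.** Both issues stand, separately. The first is a plain, undeclared contradiction between Protocol 9.5.3 and SAP 2.3.2.1. Its practical reach is probably small and is clearest for SAEs that start during screening. The second is a missing rule: an event ongoing at the first Period 2 dose that then worsens or becomes serious is absent from the Period 2 tables if it is kept on one record. On assumed rates that is roughly 1 to 7 of about 123 switched patients, before non-responders are removed.

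It is tempting to conclude that the rule favours GP2017. The documents do not show this. The rule is the same in both arms, all patients receive GP2017 in Period 2, and the existing tie-breaks send unclear events to Period 2. A distortion between arms would require worsening to be more frequent after switching than on continued GP2017, which is unknown. The loss is in what the Period 2 tables can show. How much is lost depends on eCRF completion rules that are not in these documents.

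**What to change.** 1. Restore the protocol's second limb in SAP 2.3.2.1. This costs one clause.
2. Add a Period 2 rule for both arms: an adverse event ongoing at the first Period 2 dose that increases in severity or becomes serious on or after that date is counted as a Period 2 TEAE at the new grade. Its Period 1 entry keeps the highest grade reached before that date.
3. State how the date of worsening is captured. If the eCRF does not date it, flag events ongoing at the first Period 2 dose and show them in the Period 2 tables as a separate row with their maximum grade.

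The cost is SAP wording, a derivation flag and possibly a review of the listing of events ongoing at Week 24. The downside is that a few events appear in both periods, which a table footnote should say.

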2.3.2.2 Laboratory parameters

For the identification of notable values, the laboratory manual should be consulted. The following laboratory categories will be listed.

Hematology

Blood will have been obtained at screening, baseline, week 4, week 12, week 24, week 36 and week 48 (or as required at an unscheduled visit) to measure erythrocytes, hematocrit, hemoglobin, leukocytes, platelets, basophils (absolute and percentage), eosinophils (absolute and percentage), lymphocytes (absolute and percentage), monocytes (absolute and percentage), neutrophils (absolute and percentage).

Clinical Chemistry

Blood will be obtained at screening, baseline, week 4, week 12, week 24, week 36 and week 48 (or as required at an unscheduled visit) to measure alanine aminotransferase, albumin, alkaline phosphatase, aspartate aminotransferase, total bilirubin, calcium, serum creatinine, gamma glutamyl transferase, potassium, total protein, sodium, uric acid, total cholesterol, HDL cholesterol, LDL cholesterol, rheumatoid factor, cyclic citrullinated peptide antibody, immunoglobulin A, immunoglobulin G,

Coagulation

Activated Partial Thromboplastin Time (aPTT) and INR.

Urinalysis

Dipsticks will be provided by the central laboratory to the sites for local urinalysis assessments. The sites will record the results in the appropriate eCRF page for each patient.

Measurements for density, pH, glucose, cells (RBC, WBC), proteins, blood and cylinders will be done at screening, baseline, week 4, week 12, week 24, week 36 and week 48 (or as required at an unscheduled visit).

Vital signs

Vital signs include blood pressure and heart rate measurements and will be assessed at all visits. The repeat sitting measurements will be made at 1-2 minute intervals and the mean of the three measurements will be used and entered on the corresponding eCRF page.

ECG

Standard 12-lead ECG measurements will be assessed at time points as per the study schedule (screening, week 24 and week 48). ECG results are captured in the eCRF as “Normal” “Abnormal, clinically insignificant” and “Abnormal, clinically significant”. Any abnormal clinically significant ECG findings should be recorded as adverse events.

Physical examination

A complete physical examination will include the examination of general appearance, skin, neck (including thyroid), eyes, ears, nose, throat, lungs, heart, abdomen, back, lymph nodes and extremities, as well as vascular and neurologic examination and will be done at screening, baseline, week 24 and week 48. A short physical examination with assessment of general appearance will be done at all other visits.

